4.4. Evaluation and validation design

4.4.1. Retrospective study outcomes

Table 8. Overview of the retrospective study outcomes

Outcome type	Description
Primary	
Comparison of plasma biomarker values between 2D-BioPAD prototype and benchmarking equipment.
 
Sensitivity, specificity, positive and negative predictive values of blood biomarkers measured with the 2D-BioPAD prototype for identifying:
 
 AD-related pathology (e.g., β-amyloid, tau), as indicated by CSF biomarkers measured during routine assessments at the clinical study centres using state-of-the-art equipment and established cut-offs. AD diagnosis established as per centre-specific standard procedures.
Secondary	Assessing the potential impact of other parameters, e.g., demographics, comorbidities on the primary outcomes.

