To reduce patient burden, the 2D-BioPAD clinical pilot study will use CSF biomarker values measured during standard assessment procedures at the clinical study centres. For the retrospective study, existing plasma samples will be selected from individuals who also have available CSF biomarker data. Each assay has established cut-offs for AD pathology which are used in clinical practice. The Lumipulse and Elecsys CSF AD assays have been shown to have high analytical and clinical performances²², with strong correlation and high concordance in identifying AD pathology²³.

4.1.5. *Ethical and regulatory aspects*

4.1.5.1. *Ethical aspects*

The investigators at all study centres will ensure that this study is conducted in conformance with the principles of the “World Medical Association Declaration of Helsinki” (52nd WMA General Assembly, Edinburgh, Scotland, October 2000; including the Notes of Clarification as added in 2002, Washington; 2004, Tokyo; 2008, Seoul; and 2013, Fortaleza), International Conference on Harmonisation (ICH) guidelines for Good Clinical Practice (GCP), and relevant legislation in each participating country.

Ethics Committee review

¹⁹<https://sites.uef.fi/aivobiomarkkeritutkimukset/wp-content/uploads/sites/112/2023/08/Vakuutus-Biomarkkerilaboratorio-140823.pdf>

²⁰ Pilotto A., et al. Plasma p-tau217 in Alzheimer's disease: Lumipulse and ALZpath SIMOA head-to-head comparison. medRxiv [Preprint]. 2024 May 3:2024.05.02.24306780. doi: 10.1101/2024.05.02.24306780

²¹ Dakterzada, F., et al. Assessment of the Correlation and Diagnostic Accuracy between Cerebrospinal Fluid and Plasma Alzheimer's Disease Biomarkers: A Comparison of the Lumipulse and Simoa Platforms. *Int. J. Mol. Sci.* 2024, 25, 4594. <https://doi.org/10.3390/ijms25094594>

²² Dakterzada F, et al. Assessment of the Concordance and Diagnostic Accuracy Between Elecsys and Lumipulse Fully Automated Platforms and Innostest. *Front Aging Neurosci.* 2021 Mar 4;13:604119. doi: 10.3389/fnagi.2021.604119

²³ Campbell MR, et al. P-tau/A β 42 and A β 42/40 ratios in CSF are equally predictive of amyloid PET status. *Alzheimers Dement (Amst).* 2021 May 18;13(1):e12190. doi: 10.1002/dad2.12190

The relevant clinical pilot study documents have been submitted to the following Ethics Committees as per standard local procedures:

- Regional Medical Research Ethics Committee of the Wellbeing Services County of North Savo (UEF study center, Finland)
Status: approved September 17, 2024

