4.2.1. Blood samples and selection criteria

Existing samples will be used if they are maximum 10 years old, continuously stored in -70°C freezer since collection, and there is consent for use of the samples and related clinical data, including shipping/sharing within the EU.

Table 4. Inclusion and exclusion criteria for the retrospective study

Inclusion criteria	
Plasma samples	
 • Maximum 10 years old • Up to 2 ml available for 2D-BioPAD pilot study • Stored in -70°C freezer • Existing consent to re-use for research, including shipping within the EU
Sample-related clinical data	
 • Diagnosis AD dementia, MCI due to AD, or no dementia-related disease (control) in connection to the blood sample collection time • Available data on CSF biomarkers, cognitive tests (at least MMSE), comorbidities, and medications in connection to the diagnostic workup • Existing consent to re-use data for research, including sharing within the EU
Exclusion criteria	
Sample-related clinical data	
 • Diagnosis of dementia other than AD • Mixed dementia • MCI suspected due to non-AD causes, as per clinical judgement based on centre-specific standard assessments

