4.2.3. Risk analysis

The retrospective study does not involve significant risks. It will use a total of 60 already existing plasma samples (20 per centre). Samples are already stored on-site in appropriate conditions. A smaller number of samples is considered sufficient for initial technical validation purposes in a laboratory environment. Stricter selection criteria (Table 4) are applied to ensure a well-defined case-control design, and availability of all necessary data. All clinical study centres have extensive experience and established contacts with appropriate services for biological specimen shipping.

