4.4.3. Data analysis

Analyses will include e.g.:

- Correlations (Spearman/Pearson as appropriate) between 2D-BioPAD markers and benchmarking plasma markers. Statistical tests for comparing correlation coefficients will be used where applicable.
- Linear regressions and plots of 2D-BioPAD markers and benchmarking plasma markers.
- Bland-Altman comparison of 2D-BioPAD markers against benchmarking plasma markers.

Between-group comparisons of 2D-BioPAD AD plasma biomarker levels will be conducted using e.g., Mann-Whitney U test, t-test, or ANOVA as appropriate. Groups will be defined according to both clinical and biomarker-based characteristics. Diagnostic groups will be based on diagnosis established following centre-specific standard assessments, e.g., AD dementia, other dementia, MCI, or control. Biomarker-based groups will be defined using:

- For all participants, AD blood biomarkers measured with benchmarking equipment. Cut-offs will be based on existing literature (where available) and/or data-driven, e.g., using Gaussian mixture modelling.
- For participants with available AD CSF biomarkers from standard assessments, grouping will be based on established cut-offs.
- Exploratory analyses will consider ATN-based categorizations using state-of-the-art CSF and/or benchmarking plasma biomarkers.

To assess the potential impact of other parameters, e.g., demographics, comorbidities, liver and/or kidney function, APOE genotype (where available), such parameters will be added as covariates in the analyses.

Discrimination accuracies of 2D-BioPAD AD plasma biomarkers will be determined with logistic regression models and receiver operating characteristic curve (ROC) analysis. When predicting diagnosis or CSF-based biomarker +/- status, for each AD blood biomarker the area under the receiver operating characteristic curve (AUC) of the ROCs for 2D-BioPAD and benchmarking measures will be compared with DeLong test. Sensitivity, specificity, positive and negative predictive values will be assessed for different 2D-BioPAD biomarker cut-offs. Initial analyses will consider each AD plasma biomarker individually. Further analysis will investigate combinations of plasma biomarkers to determine which combinations have the best discrimination accuracy.

AD plasma biomarkers (2D-BioPAD versus benchmarking equipment) will be investigated in relation to cognitive, clinical, and other data using appropriate regression models.

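### Table 8 makes PPV and NPV primary in the retrospective study, but in samples selected by diagnosis they carry an investigator-set case share and do not estimate predictive values in referred patients

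*Protocol*

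**What the plan says.** Table 8 (Protocol 4.4.1) has two primary items. The first compares plasma values between the prototype and the benchmarking equipment. The second is "Sensitivity, specificity, positive and negative predictive values of blood biomarkers measured with the 2D-BioPAD prototype for identifying" two targets: AD pathology as shown by CSF, and the AD diagnosis made at the centre.

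The samples come from Table 4 (4.2.1). The diagnostic entry condition is "Diagnosis AD dementia, MCI due to AD, or no dementia-related disease (control) in connection to the blood sample collection time". The exclusions are "Diagnosis of dementia other than AD", mixed dementia, and MCI thought to have a non-AD cause. CSF results are a further condition: "existing plasma samples will be selected from individuals who also have available CSF biomarker data" (4.1.4.1). Section 4.2.3 sets the number at 60, with 20 from each centre, and describes the design: "Stricter selection criteria (Table 4) are applied to ensure a well-defined case-control design".

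On analysis, section 4.4.3 says "Sensitivity, specificity, positive and negative predictive values will be assessed for different 2D-BioPAD biomarker cut-offs". It does not separate the two studies and names no reference prevalence. Table 9 (4.4.2) uses the same four measures in the prospective study, which recruits people referred for assessment.

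**The concern.** Sensitivity is calculated within cases and specificity within controls, so the ratio of cases to controls does not enter either. PPV and NPV are calculated within test-positives and test-negatives, which mix cases and controls in the proportion present in the set. When samples are selected on the target condition, that proportion is a design choice and not a prevalence.

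The CSF reference does not escape this. Samples enter by diagnosis, and section 4.1.4.1 says that CSF results are part of how the diagnosis is made. Selection by diagnosis therefore also drives the share of CSF-positive samples.

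At stake is a first-stage primary result that a reader would take as clinical performance. It would also share its name with a prospective outcome in Table 9 that means something different.

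**Working it through.** **Inputs from the protocol.** 60 samples, 20 per centre (4.2.3): 3 × 20 = 60, which reproduces. The visible text gives no group split, precision target or reference prevalence for this stage, so there is no further figure to reproduce.

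**Assumptions.** Sensitivity (Se), specificity (Sp) and the case share p are not in the protocol. They are varied below.

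**Formulas (Bayes' rule).**
- PPV = Se·p / [Se·p + (1 − Sp)(1 − p)]
- NPV = Sp(1 − p) / [Sp(1 − p) + (1 − Se)p]

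**Step 1: hold accuracy at Se = Sp = 0.85 and change only the case share.**
- p = 0.20: PPV = 0.17/(0.17 + 0.12) = 0.586; NPV = 0.68/(0.68 + 0.03) = 0.958.
- p = 2/3 (40 cases, 20 controls): 34 true and 3 false positives, so PPV = 34/37 = 0.919; 17 true and 6 false negatives, so NPV = 17/23 = 0.739.

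| Case share | PPV | NPV |
|---|---|---|
| 20% | 0.586 | 0.958 |
| 30% | 0.708 | 0.930 |
| 50% | 0.850 | 0.850 |
| 67% | 0.919 | 0.739 |

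**Step 2: other accuracies, same 60 samples.**
- Se = Sp = 0.80, 15:45 (cases:controls): PPV = 12/21 = 0.571; NPV = 36/39 = 0.923.
- Se = Sp = 0.80, 45:15: PPV = 36/39 = 0.923; NPV = 12/21 = 0.571.
- Se = Sp = 0.90: PPV goes from 0.750 at 15:45 to 0.964 at 45:15, and NPV from 0.964 to 0.750.

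**Step 3: an uninformative test.** With Se = Sp = 0.50, PPV equals the case share. At 40:20 it would be 0.67 although the test carries no information.

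**Step 4: hold the split at 40:20 and change accuracy.** Raising Se = Sp from 0.60 to 0.95 moves PPV from 0.750 to 0.974 and NPV from 0.429 to 0.905. Predictive values therefore do respond to accuracy. What they add to sensitivity and specificity is the case share alone.

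**The case against.** The strongest defence is that this stage is a laboratory technical validation within a pilot. Its results serve to improve the device (3.1), and 60 samples are considered enough for that purpose (4.2.3). PPV and NPV are two of four measures in the second primary item. Sensitivity and specificity stand beside them and do not depend on the case ratio. No visible text ties a go/no-go rule, a sample size or a test to the retrospective predictive values, and the main hypothesis in 4.4.3 concerns noninferior accuracy against benchmarking. This stands, and it lowers the severity. It does not make the two numbers interpretable. Nor can it be left to a statistical analysis plan, because the protocol itself sets both the outcome and the selection by diagnosis.

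Three stronger readings are tempting, and the document does not support them.

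- A reader might infer that PPV and NPV here reflect nothing but the case ratio. Step 4 of the working shows that they also move with sensitivity and specificity.
- A reader might infer that PPV will be overstated and NPV understated. That needs a set richer in AD than the clinics. The visible text gives neither the split nor the AD share among referred patients, and a control-rich set would reverse the direction.
- A reader might infer that the protocol leaves the split open. Figure 3, which summarises the retrospective design, is not reproduced in the text at hand and may give group numbers. A stated split would still be set by the investigators, so the point does not depend on this.

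**Conclusion.** The point holds in this form: raw PPV and NPV should not be primary outcomes of the retrospective study, for either reference. They do not estimate predictive values in referred patients and are not comparable with the PPV and NPV in Table 9. With an assumed accuracy of 85%, the same device shows PPV from 59% to 92% and NPV from 96% to 74% as the case share goes from 20% to 67%. These figures illustrate sensitivity to the case mix. They do not predict the size or direction of the error in this study, which is unknown.

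Severity is should-fix. The comparison with benchmarking equipment, sensitivity and specificity are untouched by this point, and nothing visible is decided on the retrospective predictive values.

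**What to change.** 1. In Table 8, delete the words on positive and negative predictive values from the primary outcome, for both references. Keep sensitivity and specificity and report them with exact confidence intervals.
2. If predictive values are wanted at this stage, report them only as Bayes projections, labelled as such, over a stated range of AD prevalence. State with them that Table 4 excludes non-AD dementia, mixed dementia and non-AD MCI. Specificity then rests on controls without dementia-related disease and may not transfer to the clinic.
3. In 4.4.3, restrict only the words on predictive values to the prospective study. Restricting the whole sentence would also remove sensitivity and specificity across cut-offs from the retrospective analysis.
4. Make that restriction conditional on the prospective study recruiting referred patients. Section 4.3.5.1 allows a shift there towards a case-control design if devices are short, and the same problem would then arise.

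The cost is wording in Table 8 and 4.4.3, with no new data or samples. It can go into the updated protocol due at M24 (4.1.5.2), before the retrospective study starts at M25 (4.2).

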4.4.2. Prospective study outcomes

Table 9. Overview of the prospective study outcomes

Outcome type	Description
Primary	
 Sensitivity, specificity, positive and negative predictive values of plasma biomarkers measured with the 2D-BioPAD prototype versus benchmarking equipment (same as above) for identifying AD diagnosis established as per centre-specific standard procedures. Overall experience of HCPs with the 2D-BioPAD diagnostic aid Overall experience of patients with the 2D-BioPAD diagnostic aid
Secondary	
 Comparison of plasma biomarker values between 2D-BioPAD prototype and benchmarking equipment, considering the potential impact of other parameters, e.g., demographics, comorbidities, disease stage Sensitivity, specificity, positive and negative predictive values of plasma biomarkers measured with the 2D-BioPAD prototype for identifying AD-related pathology (e.g., β-amyloid, tau), as indicated by either plasma biomarkers from benchmarking equipment or, where available, CSF biomarkers measured during routine assessments at the clinical study centres using state-of-the-art equipment. Investigating plasma biomarkers measured with 2D-BioPAD prototype versus benchmarking equipment in relation to cognitive, clinical and other data Assess if user experience (HCPs and patients) with the 2D-BioPAD diagnostic aid varies by country, clinical specialty, and/or years of experience Assess if the information provided to HCPs via the digital interface of the 2D-BioPAD diagnostic aid is understandable and relevant Collect feedback for diagnostic aid improvement from HCPs and patients

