The COVID-19 pandemic and extensive use of point-of-care (PoC) in vitro diagnostic (IVD) devices has showcased the importance of massively accessible and cost-efficient solutions for a wider range of healthcare challenges. Low-cost, reliable, and easily accessible blood-based diagnostic aids for AD are urgently needed, as diagnostic accuracy of a work-up (without support of AD biomarkers) is limited with ~25-30% misdiagnosis of AD in specialist memory clinics and >50% in primary care¹¹. Biomarker acceptance in clinical practice is also heavily dependent on healthcare professionals (HCPs) receiving the necessary support to understand what purposes biomarkers are validated for and interpret multi-marker data together with clinical data.

The 2D-BioPAD project is developing a fast, cost-effective, non-invasive, and reliable diagnostic aid for measuring blood biomarkers (Figure 2) to support the early diagnosis and progression monitoring of AD, with potential for future use in primary healthcare settings. The 2D-BioPAD diagnostic aid leverages the unique properties of 2D materials such as graphene and its derivatives. This innovative graphene-based diagnostic aid (i) introduces a versatile surface chemistry that combines nano and DNA technologies towards improved biocompatibility, stability, as well as high sensitivity and specificity for enhanced (bio-)sensing; (ii) is designed to identify and quantify in real-time and simultaneously up to 5 AD blood biomarkers; and (iii) provides an easy to use and understand digital interface with key metrics and insights regarding the measured results.

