Lumbar puncture is not done in all patients, due to contraindications, refusal of some patients to consent to an invasive and burdensome procedure, or guidelines not recommending CSF biomarkers in specific cases (e.g. no objective cognitive impairment and no other dementia risk indicators). State-of-the-art CSF biomarkers are estimated to be available via routine assessments in about 100-150 of the total 300 patients in the prospective study. Plasma biomarkers using benchmarking equipment (section 4.1.4 Benchmarking equipment for AD plasma biomarkers) will thus be measured in all 300 patients. For the retrospective study, existing plasma samples will be selected if CSF biomarker data is also available from routine assessments. Aspects related to

CSF biomarker assays used at each study centre are detailed below in section 4.1.4.1 State-of-the-art CSF biomarkers.

Blood

- Blood sampling procedures, i.e. routine sampling from all patients versus selected groups, sample storage for research purposes
- Current availability of AD blood biomarkers for routine clinical use
- Availability of kidney and liver function measurements, including list of relevant biomarkers

AD blood biomarkers are not currently available for routine clinical use at the study centres, except for plasma NFL in Finland provided by the UEF biomarker laboratory. Blood sampling is common at all study centres, especially as part of research studies. Kidney and liver function measurements are available either measured at the study centre or at primary care; creatinine and ASAT are common across all study centres.

A set of conditions for storage of existing samples applicable across study centres was identified (Table 4).

Neuroimaging

- Structural MRI procedures, i.e. routine for all patients versus selected groups
- Possibility to retrieve MRI-related data for research
- Availability and type of PET scans, and procedures (routine for all patients versus selected groups)

Structural brain MRI is done at all study centres, except in patients with MRI contraindications. Quantitative image analysis is not done as part of routine procedures but validated semi-quantitative visual rating scales (e.g. for hippocampus atrophy and white matter lesions) are used at all centres. PET scans (e.g. FDG-PET, amyloid-PET) are only done in selected cases due to higher cost.

B) Other assessments done as part of research

- Cognitive tests
- Daily life functioning level
- Other

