4.1.4. Benchmarking equipment for AD plasma biomarkers

2D-BioPAD plasma biomarker values measured in both the retrospective and prospective studies will be compared with the same plasma biomarkers (e.g., Quanterix Simoa-based) measured at the UEF Brain Research Unit biomarker laboratory¹⁷. The UEF Brain Research Unit laboratory offers diagnostic services of AD biomarkers available for physicians and hospitals since 2005 and has extensive experience with large-scale international studies on AD fluid biomarkers. Quality management system is based on international standards for quality management and for clinical laboratories¹⁸. The laboratory has ISO 15189 accreditation (FINAS

¹⁷ <https://sites.uef.fi/aivobiomarkkeritutkimukset/?lang=en>

¹⁸ <https://sites.uef.fi/aivobiomarkkeritutkimukset/>

Finnish Accreditation Service) for CSF β -amyloid 42, t-tau and p-tau analyses, which are run using automated immunoassays (Roche Elecsys).

In the EU, AD plasma biomarkers are not currently available in clinical practice on a wide scale. Finland is one of the few EU countries with available diagnostic services of AD plasma biomarkers for clinical practice, i.e., Quanterix Simoa-based plasma NfL service offered by the UEF Brain Research Unit biomarker laboratory (other Simoa-based AD plasma markers will soon become available). These in vitro diagnostic medical devices of the UEF laboratory are registered with the Finnish Medicines Agency (FIMEA, e.g.¹⁹). Other devices, reagents etc used for diagnostic services by the laboratory are CE-marked.

Depending on availability / validation status, Fujirebio Lumipulse-based plasma AD biomarkers may be considered as an alternative for benchmarking. Simoa- and Lumipulse-based plasma markers have been shown to have similar diagnostic accuracy in research studies, e.g.^{20 21}.

4.1.4.1. *State-of-the-art CSF biomarkers*

Standard assessment procedures at all three clinical study centres include CSF biomarkers measured using state-of-the-art equipment: Roche Elecsys (β -amyloid 42, t-tau and p-tau181) at UEF and GAADR, or Fujirebio Lumipulse (β -amyloid 42/40, t-tau and p-tau181) at GAADR and ZI. As lumbar puncture is an invasive procedure, CSF biomarkers are measured based on clinical indication and/or patient consent, provided that no contraindications are present. CSF biomarker information is used together with other clinical, cognitive, neuroimaging etc information to establish the diagnosis in standard clinical practice.

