Unadjusted 2-sided p-values <0.05 will be considered statistically significant. Adjustment for multiple testing using a false discovery rate (e.g., Benjamini-Hochberg procedure) will be used where relevant.

The main hypothesis is that the accuracy of the 2D-BioPAD system measurements is noninferior to the accuracy of AD plasma biomarkers measured using benchmarking equipment.

Analyses of user experience (HCPs and patients) will include mainly descriptives, with comparisons by country, clinical specialty, and/or years of experience where relevant.

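### The primary accuracy outcome takes routine centre diagnosis as truth for all patients, although half to two-thirds of those diagnoses will come mainly from work-ups without AD biomarkers, which the protocol itself calls limited; this shrinks the measured AUC gap between device and benchmark

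*Protocol*

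**What the plan says.** Section 4.4.2, Table 9, makes the first prospective primary outcome the sensitivity, specificity and predictive values of the device versus the benchmark "for identifying AD diagnosis established as per centre-specific standard procedures". It neither restricts nor splits this by how the diagnosis was reached. Section 4.4.3 adds: "The main hypothesis is that the accuracy of the 2D-BioPAD system measurements is noninferior to the accuracy of AD plasma biomarkers measured using benchmarking equipment".

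On the quality of that reference, the protocol says:

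- Section 1: "diagnostic accuracy of a work-up (without support of AD biomarkers) is limited with ~25-30% misdiagnosis of AD in specialist memory clinics".
- Section 4.1.3, on CSF: "State-of-the-art CSF biomarkers are estimated to be available via routine assessments in about 100-150 of the total 300 patients".
- Section 4.1.3, on neuroimaging: PET scans "are only done in selected cases due to higher cost".
- Section 4.1.3, on blood: "AD blood biomarkers are not currently available for routine clinical use at the study centres, except for plasma NFL in Finland".
- Section 4.1.4.1, on patients who do have CSF results: "CSF biomarker information is used together with other clinical, cognitive, neuroimaging etc information to establish the diagnosis in standard clinical practice".

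Accuracy against AD pathology is a secondary prospective outcome, judged by benchmark plasma markers "or, where available, CSF biomarkers measured during routine assessments at the clinical study centres using state-of-the-art equipment". In the retrospective study (Table 8), CSF-defined pathology is part of the primary outcome. Follow-up (sections 4.3.3.2 and 4.3.4) concentrates on patients whose diagnosis is unclear at baseline.

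**The concern.** The reference for the primary outcome mixes two kinds of label. In 100-150 patients CSF contributed to the diagnosis. In the other 150-200 (50-67%) it did not, amyloid PET will rarely fill the gap, and the label rests mainly on the kind of work-up that the Introduction describes as limited. Follow-up may correct some unclear diagnoses, but it is not aimed at confident wrong ones.

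Two things are at stake. Errors in the reference put a ceiling on the accuracy that either assay can show, so even a very good biomarker would look mediocre. They also pull the two assays' AUCs together. In a superiority comparison that would be conservative. Here the main hypothesis is noninferiority, so the distortion runs in the device's favour. The results are meant to plan confirmatory studies, so both distortions would carry forward.

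**Working it through.** **Figure in the plan.** The 300 patients rest on precedent (Table 7), with no margin, power or expected accuracy, so there is no calculation to reproduce. The counts agree: 30 + 270 = 300, and about 100 at each of three centres.

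**Inputs from the protocol.** Misdiagnosis of 25-30% without AD biomarkers; CSF in 100-150 of 300.

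**Assumptions.**
- Reference errors are independent of both assays given true status.
- CSF-informed diagnoses have 0-10% error.
- AD prevalence is 0.5.
- The label mix is similar with and without CSF.
- True AUC is 0.95 for the benchmark and 0.85 for the device, a gap of 0.10.

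**Formula.** Let PPV and NPV be those of the reference label. Taking one patient labelled AD and one labelled non-AD, and averaging over their true states:

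AUC_obs = PPV·NPV·AUC + [PPV(1-NPV) + (1-PPV)NPV]·0.5 + (1-PPV)(1-NPV)(1-AUC) = 0.5 + k(AUC - 0.5), with k = PPV + NPV - 1.

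The AUC gap between two assays is multiplied by the same k, and so is the gap in Youden's index.

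**Clinical-only patients.** The Introduction does not give the direction of error, so two readings are shown.

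| Reading | PPV | NPV | k | AUC of a perfect test | 0.10 gap seen as |
|---|---|---|---|---|---|
| Symmetric, 25% | 0.75 | 0.75 | 0.50 | 0.75 | 0.050 |
| Symmetric, 30% | 0.70 | 0.70 | 0.40 | 0.70 | 0.040 |
| Only AD labels wrong, 25% | 0.75 | 1 | 0.75 | 0.875 | 0.075 |
| Only AD labels wrong, 30% | 0.70 | 1 | 0.70 | 0.85 | 0.070 |

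**All 300, symmetric error.**
- Mildest: 150 with CSF at 0% error, 150 at 25%. Error = 37.5/300 = 0.125, k = 1 - 2(0.125) = 0.75, gap 0.075, AUC ceiling 0.875.
- Worst: 100 with CSF at 10%, 200 at 30%. Error = (10 + 60)/300 = 0.233, k = 0.533, gap 0.053, AUC ceiling 0.77.

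**All 300, only AD labels wrong.** With the same inputs k = 1 - error among AD labels, that is 1 - 0.233 = 0.767 to 1 - 0.125 = 0.875. The gap shows as about 0.077-0.088.

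**Effect on a noninferiority decision.** Simulated paired DeLong comparisons used N = 300, score correlation 0.8 or 0.9, 1,000 runs per setting and symmetric error. Noninferiority was declared when the upper limit of the two-sided 95% interval for the gap lay below the margin. The true gap was 0.10 throughout.

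| Reference | Declared, assumed margin 0.10 | Declared, assumed margin 0.05 |
|---|---|---|
| Error-free | 4-6% | 0% |
| 150 CSF at 5% error, 150 at 25% | 44-57% | 0.1% or less |
| 100 CSF at 5% error, 200 at 30% | 74-85% | about 1% |

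The direction is the same throughout, but the practical harm depends on the margin.

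**The case against.** The strongest reply is that the protocol already looks beyond routine diagnosis. Table 9 has a secondary CSF-referenced accuracy outcome. Section 4.4.3 plans the DeLong comparison of device and benchmark against CSF status as well as against diagnosis. Correlation, regression and Bland-Altman analyses compare the two assays without any diagnosis. A reader might infer that a poor device would pass unnoticed; the documents do not support that, because these analyses could expose it. What stands is that the main hypothesis is not tied to any of them. The secondary outcome also admits benchmark plasma markers as reference, and those cannot fairly judge the device against the benchmark.

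A second reply is that the 25-30% is stretched. A reader might apply it to all 300 patients, or treat it as error in both directions for every patient without CSF. The text supports neither. The figure concerns work-ups without AD biomarkers and gives no direction. Section 4.1.3 says CSF may not be recommended where there is no objective impairment, so some patients without CSF are probably easier non-AD cases. MRI ratings, consensus diagnosis for less clear cases and follow-up also help. This argues for a range and for the milder end being plausible; it does not remove the effect.

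Third, this is a declared pilot under real-world conditions, and routine diagnosis in all comers is a defensible target. That is fair, provided the result is described as what it is.

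**Conclusion.** The concern holds in a bounded form. Half to two-thirds of the primary reference labels will come mainly from work-ups without AD biomarkers, and nothing in Table 9 or section 4.4.3 separates them for the primary outcome. A true AUC gap of 0.10 would appear as about 0.053-0.075 under symmetric error and about 0.077-0.088 if only AD labels are wrong.

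A reader might infer that noninferiority is bound to succeed. That does not follow: no margin is stated here, and at an assumed 0.05 the same gap led to noninferiority in about 1% of runs or fewer under the mixed references.

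The result rests on independent errors, the assumed error of CSF-informed diagnoses and a similar label mix with and without CSF. The shrinkage is exact for AUC and Youden's index. At a fixed cut-off, a single sensitivity or specificity gap can shrink more, vanish or change sign. Plasma NfL may be an exception in Finland, where it is routine and could inform the diagnosis.

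**What to change.** In Table 9 and section 4.4.3:

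1. Report the primary sensitivity, specificity, PPV, NPV and the device-versus-benchmark AUC comparison for all patients, and also separately for diagnoses supported by CSF or amyloid PET and for clinical-only diagnoses.
2. Present the already planned DeLong comparison against CSF status beside the primary result when the noninferiority hypothesis is interpreted.
3. Describe the all-patient result as agreement with routine clinical diagnosis, not as accuracy for AD.

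This needs wording and extra tables only, since CSF and amyloid-PET results, where available, are already collected (Table 6). The cost is precision and spectrum. With about 100-150 patients in the biomarker-supported stratum, half of them with AD, the 95% half-width at a sensitivity of 0.90 is 1.96·√(0.09/50) = 0.083 to 1.96·√(0.09/75) = 0.068, against 1.96·√(0.09/150) = 0.048 for all 300. These patients are also clinically selected. The stratum should therefore inform interpretation and not be a condition that must be met before noninferiority is concluded.
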